**Amendment (b)**

This amendment is substantial because it has a significant impact on study conduct.

**Overall Rationale for the Amendment:**

This amendment to the protocol implements a CCI [REDACTED] and other non-substantial updates, including

- excluding participants with an eGFR less than or equal to CCI mL/min/CCI m^2, and
- clarification of timing and assessments included in Extended Monitoring visits and completing participants' final visits.

Section # and Name	Description of Change	Brief Rationale
1.3.1 Part A Study Schedule (Single Dose Cohorts)	Footnote b clarifies timing of, and assessments included in, Extended Monitoring visits and completing participants' final visits	Changes were made to clarify Extension Monitoring visits and completing participants' final visits
1.3.2 Part B Study Schedule (Repeat Dose Cohort)		
5.2 Exclusion Criteria	Exclusion criteria #23 changed to exclude participants with eGFR $\leq$ CCI mL/min/ CCI m 	Changes were made in response to CCI [REDACTED]
10.8.1 Blood Volumes to be Collected in Part A	Blood volume required for ADA assessment updated to CCI	Change was made to better inform total and ADA assessment blood volumes required

## 1. Protocol Summary

### 1.1. Synopsis

**Protocol Title:**

A Phase 1, Multicenter, Randomized, Placebo-Controlled, Double-Blind Trial of LY3885125 to Evaluate the Safety, Tolerability, Pharmacokinetics, and Pharmacodynamics of a Single-Ascending Dose in Participants with Dyslipidemia and Repeat-Doses in Participants with NAFLD

**Brief Title:**

A study to investigate the safety, tolerability, pharmacokinetics, and pharmacodynamics of LY3885125 compared with placebo in participants aged 18 to 70 years with dyslipidemia or NAFLD.

**Regulatory Agency Identifier Number(s):**

IND 165648

**Rationale:**

LY3885125 is a N-acetylgalactosamine (GalNAc)-conjugated small interfering ribonucleic acid (siRNA) CCI

. SCAP regulates the activation of SREBPs, which are transcription factors that govern *de novo* lipogenesis, cholesterol biosynthesis, and metabolism pathways.

CCI

This first-in-human (FIH) placebo-controlled study will evaluate the safety, tolerability, and pharmacokinetics (PK)/pharmacodynamics (PD) of single ascending subcutaneous (SC) doses of LY3885125 in participants with dyslipidemia (Part A of study), and of repeated SC doses of LY3885125 in participants with NAFLD and elevated alanine aminotransferase (ALT) (Part B of study). In Part A, the response to LY3885125 will be evaluated via changes in circulating levels of proprotein convertase subtilisin/kexin type 9 (PCSK9), CCI

**Objectives and Endpoints:**

Objectives	Endpoints
Primary	
Part A: 
 
To determine the safety and tolerability of LY3885125 after a single SC dose in participants with dyslipidemia.
 
	
 
Adverse events (AEs).
 
Serious adverse events (SAEs).
 

Part B: 
 
To determine the safety and tolerability of LY3885125 after 2 SC doses on Days [ ] and [ ] in participants with NAFLD and elevated ALT.
 
	
 
AEs.
 
SAEs.
 

Secondary	
Part A: 
 
To assess the PK and PD of LY3885125 after a single SC dose.
 
	
 
LY3885125 area under the concentration-time curve (AUC), maximum observed concentration (<math>C_{max}</math>), time of <math>C_{max}</math> (<math>T_{max}</math>).
 
Changes in PCSK9 and apolipoprotein B (ApoB) from baseline relative to placebo.
 

Part B: 
 
To assess the PK and PD of LY3885125 following 2 SC doses on Days [ ] and [ ].
 
	
 
LY3885125 AUC, <math>C_{max}</math>, <math>T_{max}</math>.
 
Relative change of liver fat content from baseline to Weeks [ ] and [ ] by MRI-PDFF compared with placebo.
 
Changes in PCSK9 and ApoB from baseline relative to placebo.
 

Objectives	Endpoints
Exploratory	
Parts A and B: 

• CCI [REDACTED]

	

• CCI [REDACTED]

• CCI [REDACTED]

Part B: 

• CCI [REDACTED]

 

• CCI [REDACTED]

	

• CCI [REDACTED]

 

• CCI [REDACTED]

## Overall Design

Study J4N-MC-YFAA is a Phase 1, multicenter, randomized, placebo-controlled, double-blind, 2-part study in participants with dyslipidemia, and participants with NAFLD and elevated ALT. The study design includes:

- **Part A (Cohorts 1 to 6):** placebo-controlled, Investigator- and participant-blind, single SC dose of LY3885125 in participants with dyslipidemia:
  - To evaluate the safety, tolerability, PK, and PD of a single ascending dose (SAD) of LY3885125 in up to [REDACTED] cohorts (Cohorts CCI).
  - CCI [REDACTED]
  - Data from Part A will inform the Part B dose.
- **Part B (Cohort 7):** placebo-controlled, Investigator- and participant-blind, repeat SC doses of LY3885125 in participants with NAFLD and elevated ALT:
  - To evaluate the safety, tolerability, PK, PD, and change of liver fat content from baseline to Weeks CCI by MRI-PDFF of a repeated dose of LY3885125 at Days CCI
  - The Part B dose will be based on data from Part A and will not exceed what has been studied in Part A. The protocol will be amended prior to initiation of Part B to define the dose and dosing frequency.

The study will begin with Part A and proceed to Part B following reviews of safety, tolerability, and available PK and PD data.

Dose escalation decisions will be made by the Dose Escalation Committee (DEC).

Recommendations to temporarily suspend study drug intervention or terminate the study early will be evaluated by a Safety Review Committee (SRC).

In both study parts, the identity of study intervention (LY3885125 or placebo) will be masked to participants, Investigators, and site-facing Sponsor personnel.

## Brief Summary

The primary purpose of this study is to determine a safe and tolerable dose of LY3885125 in participants with dyslipidemia (Part A) and in participants with NAFLD and elevated ALT (Part B).

In Part A, the approximate total duration of study participation for each participant may be up to CCI days (CC weeks), across the following study intervals:

- Screening, approximately 28 days.
- Participants will be admitted to the site on Day -1 for an inpatient treatment period of approximately CC days, during which participants will receive a single dose of LY3885125 or placebo on Day 1. The single doses planned to be administered in Part A are as follows: CCI. If more than CC mL of solution is required to deliver a dose, then it will be split into multiple injections, each with a maximum volume of CC mL.
- Participants will then attend follow-up visits as outpatients for a minimum of 25 weeks as outlined in the schedule of activities.
- If discontinuation criteria are not met as outlined in the schedule of activities, participants will continue visits for up to a total of CC weeks, as needed, including during the Monitoring Extension, unless discontinuation criteria are met.
- Each participant in Part A will be followed until the plasma concentration of CCI has returned to at least CC% of the baseline level after administration of the single dose.

In Part B, the approximate total duration of study participation for each participant may be up to CCI days (CC weeks), across the following study intervals:

- Screening, approximately 28 days.
- Participants will be admitted to the site on Day -1 for the first inpatient treatment period of approximately 2 days, during which they will receive the first dose of LY3885125 or placebo (Day 1).
- Participants will attend the first series of follow-up visits as outpatients every other week post first dose as outlined in the schedule of activities.
- Participants will be readmitted to the site on CCI for a second inpatient treatment period of approximately 2 days, during which they will receive the second dose of LY3885125 or placebo (CCI).
- Participants will then attend a second series of follow-up visits as outpatients for a minimum of CC weeks post-second dose as outlined in the schedule of activities.
- If discontinuation criteria are not met as outlined in the schedule of activities, participants will continue visits for up to a total of CC weeks post second dose, as needed, including during the Monitoring Extension, unless discontinuation criteria are met.

## Study Population:

Males, and females of nonchildbearing potential, aged 18 to 70 years, with dyslipidemia or NAFLD and CCI.

**Number of Participants:**

Enrollment for Part A will enable completion of up to [REDACTED] participants in up to 6 cohorts.

Enrollment for Part B will enable completion of approximately [REDACTED] participants in a single cohort (Cohort 7) that consists of 3 treatment arms with 2 doses administered per arm.

**Intervention Groups:*****Intervention Groups***

Participants will be sequentially enrolled into the study. After the screening period, eligible participants will be randomized to receive either LY3885125 or placebo.

Part A:

Part A Cohort	n	Randomization (LY3885125:placebo)
1-2	[REDACTED]	6:2
3-5	[REDACTED]	9:2
6 (optional)	[REDACTED]	10:9

Part B:

- Cohort 7: This is a repeat dose cohort evaluating a single dose level administered on [REDACTED] as shown in the table below. A total of [REDACTED] participants will be randomized at the start of Cohort 7 to 1 of 3 treatment arms:
  - Arm 1: Participants will receive the same dose of LY3885125 [REDACTED].
  - Arm 2: Participants will receive a dose of LY3885125 (same as in Arm 1) on [REDACTED].
  - Arm 3: Participants will receive placebo on [REDACTED].

Part B (Cohort 7) Treatment Arm	[REDACTED]	First Dose ([REDACTED]) a	Second Dose ([REDACTED]) a
1	[REDACTED]	LY3885125	LY3885125
2	[REDACTED]	LY3885125	Placebo
3	[REDACTED]	Placebo	Placebo

a The dose administered on [REDACTED] (first dose) and [REDACTED] (second dose) will be the same dose level

[figure not shown]
***Dose Modification***

Increases or decreases in dose levels or additional dose levels may be warranted as determined by the DEC, based on a review of all safety data and available PK and PD data from prior dose levels.

No dosing decision can occur without prior discussion and agreement of the DEC. If the dose escalation stopping criteria (Section 4.5.1) are met, the dose level will not be repeated or exceeded. If the temporary stopping criteria are met (Section 4.5.2), dosing in the study will be paused. The SRC will be convened in either scenario to review available data and provide recommendations regarding the continued conduct of the study.

**Safety Review Committee:** A Safety Review Committee (SRC) will be employed to review the benefit-risk profile of the LY3885125 throughout the conduct of the study. The SRC will meet **CCI** and may be convened in response to any emerging safety signal (see Safety Review Committee Charter for additional details).

## 1.2. Schema

Abbreviations: ALT = alanine aminotransferase; SAD = single ascending dose; SC = subcutaneous.

### 1.3. Schedule of Activities (SoA)

#### 1.3.1. Part A Study Schedule (Single Dose Cohorts)

Procedure	Screening	Inpatient Visit					Outpatient Follow-up Visits a							ET
							Post-Dose				Monitoring Extension b			
Week														
CCI	CCI	CCI	CCI	CCI	CCI	CCI	CCI	CCI	CCI	CCI	CCI	CCI	CCI	CCI
Informed Consent	X													
Demographics	X													
Medical history	X	X												
Review/confirm I/E criteria	X	X d												
Randomization		X												
Admit to CRU		X												
Discharge from CRU						X e								
Administer study intervention f			X											
Physical examination (PE) g	X	X												X
Symptom directed PE				X	X	X	X	X	X	X	CCI	X		
Height	X													
Weight h	X	X								X	CCI	X		X
COVID-19 PCR test i	X	X												
Pregnancy test j	X	X									CCI	X		X
FSH k	X													
Hepatic serologies l	X													
Urine drug screen and ethanol	X	X												
Urinalysis	X	X					X		X					
Safety laboratory tests	X		P	X	X	X	X	X	X	X	CCI			X
Body Temperature	X		P						X					X
Vital signs - PR/BP/RR	X		CCI	CCI	CCI	CCI	X	X	X	X	CCI	X		X
12-lead ECG m	X		CCI	CCI	CCI	CCI	X			X		X		X
Plasma PK samples n			CCI	CCI	CCI	CCI	CCI	CCI			CCI			CCI
Urine PK			CCI											
Lipid panel, (fasting) o	CCI		CCI			CCI	CCI		CCI	CCI	CCI			CCI
ApoB (fasting)			CCI			CCI	CCI		CCI	CCI	CCI			CCI
Stored samples (fasting)			P				X	X	X	X	D43, 57, 85, 169			
ISR assessments			Following spontaneous report from participant, complete ISR CRF and Pain VAS assessment											
Immunogenicity			CCI					CCI		CCI	CCI			CCI
AE/concomitant medications	X	X	X	X	X	X	X	X	X	X	CCI	X		X

PCSK9	X		P			X	X	X	X	X	CCI	X	X
HbA1c	X		P						X		CCI		X

Abbreviations: AE = adverse event; ApoB = apolipoprotein B; BP = blood pressure; COVID-19 = Coronavirus disease 2019; CRF = case report form; CRU = clinical research unit; D = day; ECG = electrocardiogram; ET = early termination; h = hour(s); FSH = follicle-stimulating hormone; HCV = hepatitis C virus; HDL-C = high-density lipoprotein cholesterol; I/E = inclusion/exclusion; ISR = injection-site reaction; LDL-C = low-density lipoprotein cholesterol; CCI min = minutes; P = predose; PCSK9 = proprotein convertase subtilisin/kexin type 9; PCR = polymerase chain reaction; PD = pharmacodynamics; PE = physical examination; PK = pharmacokinetics; PR = pulse rate; Q2W = once every 2 weeks; PUC = preparative ultracentrifugation; Q4W = once every 4 weeks; RR = respiration rate; SC = subcutaneous; TEAE = treatment-emergent AE; TG = triglyceride; VAS = visual analog score; VLDL-C = very low-density lipoprotein cholesterol.

- a All follow-up visits should take place in the morning after an overnight fast of at a minimum **CCI** hours. Water is permitted *ad libitum* during the fasting period.
- b After Day **CCI**, once any treatment related AEs are resolved and PCSK9 levels return to at least **CCI**% of baseline, the Monitoring Extension visits may be discontinued. The final visit of a participant who completes the study will be the first scheduled Monitoring Extension visit after they report no ongoing AEs, and after PCSK9 levels have returned to at least 80% of baseline in a blood sample collected at one of the preceding visits. At the participant's final visit, they will receive the assessments performed at ET, except for the collection of a blood sample for PCSK9 assessment.
- c Outpatient follow-up visits on Days **CCI** will be conducted through a remote telehealth visit assessing AE/concomitant medications.
- d On Day -1 prior to randomization review AEs, concomitant medications, and compliance to Inclusion/Exclusion criteria.
- e Discharge from CRU after all assessments have been completed.
- f All doses of study intervention will be administered SC in the morning after an overnight fast of approximately 8 hours duration.
- g Complete physical examination performed at Screening, ET and last visit., and symptom-directed examinations at all other visits.
- h Body weight is measured at any time before breakfast.
- i A COVID-19 PCR test will be performed at Screening and on Day -1 prior to dosing. If test results are positive for the virus the participant will be excluded from the study.
- j A serum pregnancy will be performed at screening. Urine pregnancy tests may be performed at all other visits. If a urine test result is positive, the result will be confirmed with a serum test.
- k A serum FSH test will be performed in women at screening to confirm postmenopausal status.
- l If the HCV antibody test is positive, it must be followed by an HCV RNA test. Participants who are positive for HCV antibody and negative for HCV RNA may be enrolled. See Exclusion Criterion #8, Section 5.2.
- m Single 12-lead ECG at screening, safety follow-up and ET visit. Three triplicate 12-lead ECGs at pre-dose 2 minutes apart to establish baseline. Triplicate 12-lead ECGs at all other scheduled times. The actual day and time must be documented in the CRF.
- n PK samples identified with an X may be obtained at any time within the scheduled days; the exact date and time of blood sample collection must be recorded in the CRF.
- o Lipid panel: TG, total cholesterol, LDL-C (PUC), VLDL-C (calculated), HDL-C, non-HDL-C (calculated).

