### 2.2.1. Summary of Nonclinical Data

The cynomolgus monkey and Sprague Dawley rat were selected as the species for safety assessment. Due to the homology of the SCAP mRNA target sequence with humans, cynomolgus monkeys (and not rat) are pharmacologically responsive to LY3885125 and allow assessment of adverse effects related to the intended pharmacologic activity. This species selection strategy allows for evaluation of off-target and oligonucleotide-related class effects in both species and potential exaggerated pharmacology in monkeys. This is an accepted approach for the safety evaluation of oligonucleotides (Kornbrust et al. 2013; FDA/CDER Onpatro NDA 210922).

A single-dose monkey study CCI was conducted to assess cytokine and complement activation after a single administration of LY3885125. Administration of CCI or CCI mg/kg LY3885125

to male cynomolgus monkeys (*Macaca fascicularis*) once via SC injection resulted in no LY3885125-related effects on mean body weight, clinical observations, coagulation or clinical chemistry parameters, or effects on cytokine (CCI) and complement (CCI) parameters.

A standalone cardiovascular study was conducted to evaluate the potential cardiovascular effects of LY3885125 in instrumented male cynomolgus monkeys (CCI). CCI male cynomolgus monkeys were administered by SC injection single doses of control CCI or CCI mg LY3885125/kg via SC injection (1 males per group).

No LY3885125-related qualitative electrocardiogram (ECG) abnormalities or quantitative changes in PR interval, QRS duration, QT interval, or individual heart rate-adjusted QT (QTc) interval were noted up to CCI postdose following administration of CCI.

Monkeys administered CCI LY3885125 were noted to have a transient increase in heart rate (of up to CCI bpm) from CCI hours postdose, which resolved by CCI postdose; a transient increase in systolic (CCI), diastolic (CCI), and mean arterial blood pressure CCI from CCI postdose, which resolved by CCI; and an increase in body temperature (CCI) from CCI postdose, which resolved by CCI postdose. No heart rate, blood pressure, or body temperature changes were noted in monkeys administered CCI.

No LY3885125-related changes in arterial pulse pressure or dP/dtmax (maximal rate of rise in pressure), or changes in locomotor activity were noted up to CCI following administration of CCI.

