**Table 2.2 Important Potential Safety Risks with LY3885125**

Potential Risk of Clinical Significance	Summary of Data/Rationale for Risk	Mitigation/Monitoring Strategy
Hypersensitivity or allergic reactions	Not specific to LY3885125. Oligonucleotide therapies, both marketed and those in development, have been associated with hypersensitivity events.	Monitor for hypersensitivity reactions in participants. Assess spontaneously reported adverse events for their likelihood to represent hypersensitivity reactions. Once identified, investigative site personnel will collect additional information to characterize the type of reaction using standardized forms. Qualified staff will have received training and have access to supportive measures to manage the reactions.
Injection-site reactions	Not specific to LY3885125. As this molecule is an injectable therapeutic, there is the potential risk of localized injection-site reactions.	Qualified staff will have received training and have access to supportive measures to manage the reactions.
CCI [REDACTED]	Specific to LY3885125. CCI [REDACTED] [REDACTED] Further information is provided in the IB.	Vital signs and ECG will be recorded across multiple scheduled time points following single and multiple doses.
CCI [REDACTED]	CCI [REDACTED] [REDACTED] CCI [REDACTED]	CCI [REDACTED] [REDACTED]

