#### 4.1.1.2. Treatment Period (Part A)

In each period, participants will be admitted to the clinical research unit (CRU) on the day prior to dosing (Day -1) for 4 overnight stays. Participants will be monitored as inpatients in the CRU up to Day 1.

Participants will be given a SC dose of LY3885125 or placebo on Day 1.

The single doses planned to be administered in Part A are as follows: [REDACTED] mg, [REDACTED] mg, [REDACTED] mg, [REDACTED] mg, and [REDACTED] mg.

The safety data to be reviewed at each dose level will include, but are not limited to, AEs, clinical laboratory safety tests, vital signs, ECGs, physical examination (symptom-directed). The dose level for each cohort may be adjusted based on emerging safety, tolerability, and available PK and PD data from preceding cohorts.

After review of these data, the DEC will decide if the planned dose needs to be modified. The magnitude of dose escalations may be reduced following data review.

The conduct of DEC meetings is described in Section 6.3.1, the dose escalation stopping criteria are described in Section 4.5.1, and the temporary stopping criteria are described in Section 4.5.2.

Details of assessments and their timing in Part A are provided in the SoA (Section 1.3.1) and in Section 8 (study assessments and procedures).

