### 5.11.5 Vital Signs

Descriptive statistics for observed values and changes from baseline in the following vital signs will be presented by treatment group and visit:

- Systolic blood pressure (mmHg)
- Diastolic blood pressure (mmHg)
- Pulse rate (bpm)
- Respiration rate (breath / min)
- Body temperature (degrees Celsius)
- Body weight (kg)

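### Part A schedules no post-dose body temperature before the third outpatient visit, so an early asymptomatic rise would be found only by unscheduled measurement or AE report and could not be compared with placebo.

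*Protocol*

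**What the plan says.** **Nonclinical finding.** Protocol 2.2.1 describes a single-dose cardiovascular study in instrumented monkeys. One dosed group had transient rises in heart rate and blood pressure, "and an increase in body temperature (CCI) from CCI postdose, which resolved by CCI postdose". The same section adds: "No heart rate, blood pressure, or body temperature changes were noted in monkeys administered CCI". Doses, sizes and times are redacted.

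**Risk table.** For a risk described as specific to the drug, whose name is redacted, protocol Table 2.2 gives this mitigation: "Vital signs and ECG will be recorded across multiple scheduled time points following single and multiple doses".

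**Part A schedule (protocol 1.3.1).** The repeated row is "Vital signs - PR/BP/RR", that is pulse rate, blood pressure and respiration rate. "Body Temperature" is a separate row with entries at screening, predose on the dosing day, the third outpatient column and ET. Footnote b adds the ET assessments at a completing participant's final visit. Participants are admitted "on the day prior to dosing (Day -1) for 4 overnight stays" (protocol 4.1.1.2).

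**Unscheduled routes.** Protocol 8.2.2 allows vital signs when clinically indicated, in both parts. Protocol 8.2.8 asks for temperature when fever or a blood pressure change accompanies a hypersensitivity reaction.

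**SAP.** Section 5.11.5 counts body temperature among the vital signs summarised by treatment group and visit, as observed value and change from baseline. Section 5.2.8 tabulates only scheduled post-baseline vital signs. Section 5.2.3 keeps ET assessments in listings.

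**The concern.** Three changes appeared together in the monkeys. After dosing, the schedule follows two of them through the inpatient stay and leaves out the third, although the participants are still in the unit and the other vital signs are being taken.

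Safety and tolerability is the primary objective, and the Dose Escalation Committee reviews vital signs before each step up in dose. If the drug caused a short, symptomless rise in temperature, the committee would have no systematic readings to show it, and the final tables could not compare active with placebo in that period. A reader of the SAP 5.11.5 temperature summary could take an unremarkable table as reassurance about an acute effect that the schedule was not set up to measure.

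**Working it through.** There is no power or error-rate figure to reproduce. The check is a reading of the schedule and a count of participants.

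**1. Columns of the Part A schedule.** 1 screening + 5 inpatient + 4 outpatient post-dose + 3 monitoring extension + 1 ET = 14. Three other rows confirm the alignment: dosing falls in column 3, discharge in column 6 (the last inpatient column), and post-dose urinalysis in columns 7 and 9.

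**2. Rows side by side.**

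| Columns | Body temperature | PR/BP/RR |
|---|---|---|
| 1 (screening) | yes | yes |
| 3 (dosing day) | predose only | entry, times redacted |
| 4, 5, 6 (later inpatient) | blank | entry in each |
| 7, 8 (first two outpatient) | blank | entry in each |
| 9 (third outpatient) | yes | yes |
| 10 (fourth outpatient) | blank | yes |
| 11, 12 (extension) | blank | entry in each |
| 14 (ET) | yes | yes |

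**3. Are the blanks redactions?** No. Redacted cells in this table carry a redaction mark, as the inpatient cells of the PR/BP/RR row do. The temperature cells are empty.

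**4. Count.** The post-dose columns before the third outpatient visit are 4, 5, 6, 7 and 8. Temperature is scheduled in 0 of 5 and PR/BP/RR in 5 of 5. No temperature is scheduled after the dose on the dosing day either.

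**5. Participants affected.** Reading the ratios as counts for Cohorts 1 to 5:
- active: 6 + 6 + 9 + 9 + 9 = 39
- placebo: 2 × 5 = 10
- total: 39 + 10 = 49

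Protocol 9.5 agrees: 68 planned for Part A less 19 for Cohort 6 gives 68 − 19 = 49.

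**6. What reaches the SAP table.** A temperature taken in the unit because staff suspected something is unscheduled, so it is listed only (SAP 5.2.8). ET values are listed only (SAP 5.2.3). Before the monitoring extension, the one scheduled post-dose value available to the SAP 5.11.5 summary is the third outpatient visit.

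**7. Part B as designed (protocol 1.3.2).** Temperature is scheduled at screening, predose at each of the two doses, and ET. A footnote allows further readings when clinically indicated.

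**The case against.** A reader might infer that the study cannot detect a temperature rise at all. The documents do not support that. Protocol 8.2.2 permits clinically indicated vital signs in Part A as well as Part B, so hypersensitivity is not the only trigger. Symptom-directed examinations fall on the later inpatient days, AEs are reviewed throughout the stay, and a clinically significant vital-sign abnormality counts as an AE. The accompanying heart rate and blood pressure rises have scheduled monitoring. A sustained rise could show at the third outpatient visit. Protocol 4.1 also lets safety measurement schedules be adjusted after ongoing reviews. All of this stands. It covers a suspected, symptomatic or lasting rise, but not a short one without symptoms.

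A reader might also infer that the schedule contradicts Table 2.2. That is not shown. The name of the risk is redacted, the mitigation does not mention temperature, and another row of the table is redacted and could hold a rationale. What can be said is that protocol 2.2.1 names temperature openly and protocol 1.3.1 does not follow it early.

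Nor do the documents prove that the third outpatient visit comes after any rise would have resolved. Onset, resolution and visit days are all redacted. The finding was absent in another dosed group, and with the safety margins redacted its relevance at the study doses cannot be judged.

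Finally, the SAP introduction says the study was discontinued after Cohort 5, so a schedule change cannot recover data for those participants. That limits what the schedule change can achieve. It does not affect how the existing table should be read.

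**Conclusion.** The concern holds in a limited form. Part A has no scheduled temperature from dosing until the third outpatient visit (0 of 5 columns), for about 39 active and 10 placebo participants in the five cohorts. An early asymptomatic rise would be found only by unscheduled measurement or AE report, and the SAP 5.11.5 table could not compare it with placebo.

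This rests on two assumptions. The first is that a rise in humans, if there is one, would come and go early, as the resolution in a single-dose monkey study suggests; the redacted times prevent a direct check. The second is that the randomization ratios give the cohort counts, which the protocol's total of 68 supports.

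The point is a low-cost improvement to safety capture and a caution about interpretation. It does not show that a safety signal was missed.

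**What to change.** **Schedule.** Reconcile protocol 1.3.1 and 1.3.2 with section 2.2.1 and Table 2.2 by recording body temperature at the inpatient time points where PR/BP/RR is already taken. This applies to the protocol as designed and to any later protocol that reuses the schedule. The cost is one thermometer reading at existing assessments and an edit to one row of each schedule. The downside is a few more queries about transient readings.

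**Data already collected.** In the SAP or clinical study report:
- summarise unscheduled temperatures and pyrexia AEs by arm, noting that these readings were prompted by suspicion and that an arm comparison is descriptive only;
- state with the SAP 5.11.5 temperature table that no post-dose temperature was scheduled before the third outpatient visit, and do not present the table as evidence of no acute effect.

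The unscheduled values are already to be listed, and the AE tables already report by preferred term, so this needs one short summary and a footnote. If the database is locked, SAP section 5 already provides an addendum for added analyses.
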